### 6.3 Treatment Period – Day 1 Through End of Treatment

All patients will receive IV treatment for a minimum of 28 doses of ETX2514SUL plus 28 doses of imipenem/cilastatin or 14 doses of colistin plus 28 doses of imipenem/cilastatin (ie, 7 days of antibiotics for those without dose adjustments). Patients can receive up to 14 days of IV treatment if clinically indicated. Time of discontinuation of antibiotics will be determined on achievement of clinical cure (see [Section 7.6](#)). Additionally, at any time during the study, if a patient develops signs and symptoms of disease worsening, cultures from all appropriate sites should be collected and sent to the central laboratory.

#### 6.3.1 Day 1

The following procedures will be performed at Day 1:

- Record concomitant medications;
- Obtain vital signs, including blood pressure, heart rate, and respiratory rate, and, for ventilated patients, oxygen therapy and respiratory settings including FiO2 and PEEP;
- Assess clinical signs and symptoms (see [Section 7.5](#));
- Collect predose blood samples for:
  - Serum chemistry;
  - Serum creatinine;
  - Hematology; and
  - Blood cultures in patients with bacteremia, if applicable;
- Collect predose urine sample for urinalysis;
- Calculate APACHE II, SOFA, or qSOFA score prior to randomization;

Note: An APACHE II or SOFA score will be calculated prior to randomization for patients in Part A only. For patients who are not being treated in an intensive care unit and cannot have an APACHE II or SOFA score performed, and for all patients in Part B, a qSOFA score should be calculated.

- Randomize patient to study drug via IRT;
- Administer study drug;
- For intense PK sampling, collect PK samples after the second infusion at the end of the infusion after the infusion pump is turned off (+15 minutes), 1.5 hours ( $\pm$ 15 minutes) after the end of the infusion, and immediately prior to the start of the next infusion;

- For sparse PK sampling, collect PK samples after the second infusion, immediately prior to the start of the next infusion. The patient should have received at least 2 infusions before this schedule is implemented;

Note: When possible, PK samples should be collected after the second infusion on Day 1. If the second infusion happens during the night and it is not possible to collect the PK sample after the infusion, the same procedures could be done after the third infusion on Day 1. The PK sample should be taken after the patient received at least 2 infusions on Day 1.

- Perform 12-lead ECG at the end of the first infusion of study drug for all patients, and consult the study Medical Monitor and local cardiologist in cases of clinically significant abnormal findings (eg, a QTcF  $\geq 480$  msec after the end of infusion and after the patient has been in a supine position for at least 10 minutes); and
- Assess adverse events.

### 6.3.2 Day 2

The following procedures will be performed at Day 2:

- Record concomitant medications;
- Perform a limited physical examination, if needed;
- Obtain vital signs, including blood pressure, heart rate, and respiratory rate, and, for ventilated patients, oxygen therapy and respiratory settings including FiO2 and PEEP;
- Assess clinical signs and symptoms (see [Section 7.5](#));
- Collect blood samples for:
  - Serum creatinine; and
  - Blood cultures in patients with bacteremia, if applicable;
- Administer study drug; and
- Assess adverse events.

### 6.3.3 Day 3

The following procedures will be performed at Day 3:

- Record concomitant medications;
- Perform a complete physical examination, including weight;
- Obtain vital signs, including blood pressure, heart rate, and respiratory rate, and, for ventilated patients, oxygen therapy and respiratory settings including FiO2 and PEEP;
- Assess clinical signs and symptoms (see [Section 7.5](#));
- Collect blood sample for:
  - Serum chemistry;
  - Serum creatinine;

- Hematology; and
- Blood cultures in patients with bacteremia, if applicable;
- Collect urine sample for urinalysis;
- Administer study drug;
- For intense PK sampling, if PK samples will not be collected on Day 4, collect PK samples at the end of any infusion after the infusion pump is turned off (+15 minutes), and immediately prior to the start of the next infusion;
- For sparse PK sampling, if PK samples will not be collected on Day 4, collect PK samples after the end of infusion, immediately prior to the start of the next infusion;

Note: When possible, PK samples should be collected on Day 4. If collection on Day 4 is not possible, post-dose PK samples may be collected on Day 3 or Day 5 instead of Day 4, at the discretion of the Investigator.

- If PK samples are collected, repeat 12-lead ECG as close as possible following the end of the infusion of study drug administration associated with the PK samples, if clinically indicated; and
- Assess adverse events.

#### 6.3.4 Day 4

The following procedures will be performed at Day 4:

- Record concomitant medications;
- Perform a limited physical examination, if needed;
- Obtain vital signs, including blood pressure, heart rate, and respiratory rate, and, for ventilated patients, oxygen therapy and respiratory settings including FiO2 and PEEP;
- Assess clinical signs and symptoms (see [Section 7.5](#));
- Collect blood samples for:
  - Serum creatinine; and
  - Blood cultures in patients with bacteremia, if applicable;
- Administer study drug;
- For intense PK sampling, collect PK samples at the end of any infusion after the infusion pump is turned off (+15 minutes), and immediately prior to the start of the next infusion;
- For sparse PK sampling, collect PK samples after the end of infusion, immediately prior to the start of the next infusion;

Note: When possible, PK samples should be collected on Day 4. If collection on Day 4 is not possible, post-dose PK samples may be collected on Day 3 or Day 5 instead of Day 4, at the discretion of the Investigator.

- If PK samples are collected, repeat 12-lead ECG as close as possible following the end of the infusion of study drug administration associated with the PK samples, if clinically indicated; and
- Assess adverse events.

#### 6.3.5 Day 5

The following procedures will be performed at Day 5:

- Record concomitant medications;
  - Perform a complete physical examination, including weight;
  - Obtain vital signs, including blood pressure, heart rate, and respiratory rate, and, for ventilated patients, oxygen therapy and respiratory settings including FiO2 and PEEP;
  - Assess clinical signs and symptoms (see [Section 7.5](#));
  - Assess clinical outcome. In Part A, clinical outcome will be assessed by the blinded assessor, in addition to the unblinded Investigator (see [Section 7.6](#));
  - Collect blood sample for:
    - Serum chemistry;
    - Serum creatinine;
    - Hematology; and
    - Blood cultures in patients with bacteremia, if applicable;
  - Collect urine sample for urinalysis;
  - Collect infection site-specific cultures based on diagnosis if clinically indicated (see [Section 7.7](#));
  - Administer study drug;
  - For intense PK sampling, if PK samples were not collected on either Day 3 or Day 4, collect PK samples at the end of any infusion after the infusion pump is turned off (+15 minutes), and immediately prior to the start of the next infusion;
  - For sparse PK sampling, if PK samples were not collected on either Day 3 or Day 4, collect PK samples after the end of infusion, immediately prior to the start of the next infusion;
- Note: When possible, PK samples should be collected on Day 4. If collection on Day 4 is not possible, post-dose PK samples may be collected on Day 3 or Day 5 instead of Day 4, at the discretion of the Investigator.
- If PK samples are collected, repeat 12-lead ECG as close as possible following the end of the infusion of study drug administration associated with the PK samples, if clinically indicated; and
  - Assess adverse events.

### 6.3.6 Day 6

The following procedures will be performed at Day 6:

- Record concomitant medications;
- Perform a limited physical examination, if needed;
- Obtain vital signs, including blood pressure, heart rate, and respiratory rate, and, for ventilated patients, oxygen therapy and respiratory settings including FiO2 and PEEP;
- Assess clinical signs and symptoms (see [Section 7.5](#));
- Collect blood sample for:
  - Serum creatinine; and
  - Blood cultures in patients with bacteremia, if applicable;
- Administer study drug; and
- Assess adverse events.

### 6.3.7 Day 7 to Day 14 and End of Treatment Visit

Patients will be treated with 28 doses of ETX2514SUL plus 28 doses of imipenem/cilastatin or 14 doses of colistin plus 28 doses of imipenem/cilastatin (ie, 7 days for those without dose adjustments), with a prolongation of therapy up to 14 days if clinically indicated.

If EOT occurs on Day 7, Day 7 study procedures may be considered the EOT Visit study procedures. If EOT occurs after Day 7, the EOT Visit activities should be completed within 24 hours after the last dose of study drug. Day 7 to Day 14 study procedures are only required if the patient receives IV study drug treatment on Day 7 to Day 14. If EOT has already occurred, study procedures are not required to be performed.

The following procedures will be performed at Day 7 to Day 14 and at the EOT Visit:

- Record concomitant medications;
- Perform a complete physical examination, including weight (Day 7 and EOT Visit only);
- Perform a limited physical examination, if needed (Day 8 to Day 14 only);
- Obtain vital signs, including blood pressure, heart rate, and respiratory rate, and, for ventilated patients, oxygen therapy and respiratory settings including FiO2 and PEEP;
- Assess clinical signs and symptoms (see [Section 7.5](#));
- Assess clinical outcome. In Part A, clinical outcome will be assessed by the blinded assessor, in addition to the unblinded Investigator (see [Section 7.6](#)) (Day 7 and EOT Visit only);
- Perform a highly sensitive urine or serum pregnancy test for women of childbearing potential only (EOT Visit only);
- Collect blood sample for:
  - Serum chemistry (Day 7 and EOT Visit only);
  - Serum creatinine;

- Hematology (Day 7 and EOT Visit only); and
- Blood cultures in patients with bacteremia, if applicable;
- Collect urine sample for urinalysis (Day 7 and EOT Visit only);
- Perform 12-lead ECG and consult the study Medical Monitor and local cardiologist in cases of clinically significant abnormal findings (eg, a QTcF  $\geq$ 480 msec) (EOT Visit only);
- Collect infection site-specific cultures based on diagnosis if clinically indicated (see [Section 7.7](#)) (Day 7 and EOT Visit only);
- Administer study drug; and
- Assess adverse events.

#### **6.4 Test of Cure Visit**

The TOC Visit will occur 7 days ( $\pm$ 2 days) after the EOT Visit.

The following procedures will be performed at the TOC Visit:

- Record concomitant medications;
- Perform a limited physical examination, if needed;
- Obtain vital signs, including blood pressure, heart rate, and respiratory rate, and, for ventilated patients, oxygen therapy and respiratory settings including FiO2 and PEEP;
- For patients with HABP, VABP, or VP, perform chest X-ray, MRI, or CT scan;
- Assess clinical signs and symptoms (see [Section 7.5](#));
- Assess clinical outcome. In Part A, clinical outcome will be assessed by the blinded assessor, in addition to the unblinded Investigator (see [Section 7.6](#));

Note: If a patient is a clinical failure at EOT, the patient is automatically considered a failure at the TOC Visit and LFU Visit, and the assessment of clinical response by the Investigator should be listed as “failure at EOT or TOC.”

- Collect blood samples for:
  - Serum chemistry;
  - Serum creatinine;
  - Hematology; and
  - Blood cultures in patients with bacteremia, if applicable;
- Collect urine sample for urinalysis;
- Collect infection site-specific cultures based on diagnosis if clinically indicated (see [Section 7.7](#)); and
- Assess adverse events.

## 6.5 Late Follow-Up and Day 28 Visit

The LFU Visit will occur 14 days ( $\pm 2$  days) following the EOT Visit. The LFU Visit should be performed as an in-person visit; however, if the patient is unable to attend the LFU Visit at the site, the patient may be contacted by telephone call for follow-up assessment of concomitant medications, clinical signs and symptoms, and adverse events. ***All patients who are alive and have not withdrawn consent for participation in the study must be contacted at Day 28 or anytime thereafter to assess survival if their LFU Visit is prior to Day 28.***

The following procedures will be performed at the LFU Visit:

- Record concomitant medications;
- Perform a limited physical examination, if needed;
- Obtain vital signs, including blood pressure, heart rate, and respiratory rate, and, for ventilated patients, oxygen therapy and respiratory settings including FiO2 and PEEP;
- Assess clinical signs and symptoms (see [Section 7.5](#));
- Assess clinical outcome. In Part A, clinical outcome will be assessed by the blinded assessor, in addition to the unblinded Investigator (see [Section 7.6](#));

Note: If a patient is a clinical failure at EOT, the patient is automatically considered a failure at the TOC Visit and LFU Visit, and the assessment of clinical response by the Investigator should be listed as “failure at EOT or TOC.”

- Collect blood samples for:
  - Serum chemistry;
  - Serum creatinine;
  - Hematology; and
  - Blood cultures in patients with bacteremia, if applicable;
- Collect urine sample for urinalysis;
- Collect infection site-specific cultures based on diagnosis if clinically indicated (see [Section 7.7](#)); and
- Assess adverse events.

## 6.6 Early Termination Visit/Withdrawal Procedures

For patients who are withdrawn from the study prior to completion of study drug treatment or discontinue study drug prematurely, an Early Termination (ET) Visit should be completed at the time of study withdrawal or study drug discontinuation. Patients who discontinue study drug prematurely but are not withdrawn from the study should complete TOC and LFU Visits. Patients who are randomized to Part A based on a positive screening of a respiratory sample for ABC by BPP rapid test, but subsequently do not have growth of ABC in their respiratory sample culture processed by the local microbiology laboratory, will be considered withdrawn from the study drug treatment. For patients who are withdrawn from the study after the EOT Visit but prior to completion of the study, the next scheduled visit (either the TOC Visit or LFU Visit) should be completed at the time of study withdrawal. An assessment of all-cause mortality at Day 28 or

anytime thereafter must be made for all patients initially randomized to the study (including HABP/VABP/VP patients who are randomized to Part A based on a positive BPP rapid test, but who subsequently do not have growth of ABC in their respiratory sample culture), regardless of the duration of study drug received, as long as there has been no withdrawal of consent. See [Section 4.3](#) for complete details on criteria for withdrawal and/or discontinuation.

The following procedures will be performed at the ET Visit:

- Record concomitant medications;
- Perform a complete physical examination, including weight;
- Obtain vital signs, including blood pressure, heart rate, and respiratory rate, and, for ventilated patients, oxygen therapy and respiratory settings including FiO2 and PEEP;
- Assess clinical signs and symptoms (see [Section 7.5](#));
- Assess clinical outcome. In Part A, clinical outcome will be assessed by the blinded assessor, in addition to the unblinded Investigator (see [Section 7.6](#));
- Perform a highly sensitive urine or serum pregnancy test for women of childbearing potential only;
- Collect blood sample for:
  - Serum chemistry;
  - Serum creatinine;
  - Hematology; and
  - Blood cultures in patients with bacteremia, if applicable;
- Collect urine sample for urinalysis;
- Perform 12-lead ECG and consult the study Medical Monitor and local cardiologist in cases of clinically significant abnormal findings (eg, a QTcF  $\geq$ 480 msec);
- Collect infection site-specific cultures based on diagnosis if clinically indicated (see [Section 7.7](#)); and
- Assess adverse events.

## **7 EFFICACY ASSESSMENTS**

### **7.1 Primary Efficacy Endpoint**

The primary efficacy endpoint for the study is 28-day all-cause mortality in the CRABC m-MITT Population in Part A.

### **7.2 Secondary Efficacy Endpoints**

The secondary efficacy endpoints for Part A and Part B include the following:

- 28-day all-cause mortality in the Intent-to-Treat (ITT) Population;
- Clinical cure at TOC in the CRABC m-MITT Population;
- Clinical cure at TOC in the m-MITT, Clinical Evaluable (CE), Microbiologic Evaluable (ME), and CRABC ME Populations;
- Clinical cure at Day 5, Day 7, EOT, and LFU in the m-MITT, CRABC m-MITT, CE, ME, and CRABC ME Populations;
- Microbiological favorable assessment at Day 5, Day 7, EOT, TOC, and LFU in the m-MITT, CRABC m-MITT, ME, and CRABC ME Populations;
- 14-day all-cause mortality in the CRABC m-MITT and m-MITT Populations;
- 28-day all-cause mortality in the m-MITT and CRABC ME Populations; and
- PK exposure of ETX2514 and sulbactam in the PK Population.

### **7.3 Other Efficacy Endpoints**

The exploratory efficacy endpoints include the following:

- Clinical cure based on PK exposure;
- Clinical cure based on MIC distribution of ETX2514SUL;
- Clinical cure based on baseline resistance to ETX2514SUL, carbapenems, or colistin;
- Number of days in the intensive care unit;
- Number of patients transferred to the intensive care unit;
- For patients with VABP, VP, or ventilated HABP, number of days on ventilators;
- Number of days in the hospital; and
- Number of days on study drug treatment.

### **7.4 Assessment of 28-Day Survival**

Every attempt must be made to record survival status at Day 28 or anytime thereafter for all randomized patients (including HABP/VABP/VP patients who are randomized to Part A based on a positive BPP rapid test, but who subsequently do not have growth of ABC in their respiratory sample culture), regardless of their status of treatment, as long as the patient has not withdrawn consent from participation in the study. An in-person assessment is preferred; however, this assessment may also be performed via a telephone call if an in-person visit is not possible.

For patients with an LFU Visit occurring before Day 28, a telephone call to assess survival will be made on Day 28 or anytime thereafter.

## **7.5 Assessment of Clinical Signs and Symptoms**

Clinical signs and symptoms of the presenting indication will be assessed at Screening, daily during IV treatment beginning on Day 1, at the EOT Visit, at the TOC Visit, at the LFU Visit, and at the ET Visit, if applicable, by the blinded assessor and the unblinded Investigator for Part A and by the unblinded Investigator for Part B. When possible, the same study personnel should complete the assessments at approximately the same time each day. Maximum daily temperature (defined as the maximum temperature reported on a single treatment day) will be recorded. Body temperature may be taken per the site's preferred method, as specified in [Table 3](#), and will be recorded in the appropriate eCRF. The same method of measuring a patient's body temperature should be used throughout the study.

Each sign and/or symptom of the presenting indication will be assigned a classification of absent, mild, moderate, or severe. Findings from the assessment of signs and symptoms will be captured on the appropriate eCRF and should not be documented as adverse events. The signs and symptoms by indication are presented in [Table 3](#).

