Although sulbactam is available as a standalone product in a small number of countries (eg, Combactam, Germany), the vast majority of human use is in combination with BLs (eg, Unasyn, combination of ampicillin/sulbactam). The clinical safety of sulbactam has been established by nearly 30 years of experience with Unasyn. Based on the product label, Unasyn is generally safe and well tolerated. The dose of sulbactam that will be used in combination with ETX2514 is the highest dose approved for human use (1.0 g q6h, maximum daily dose in patients with normal renal clearance of 4.0 g). The most frequently reported adverse events reported with Unasyn are nausea, vomiting, diarrhea, pain at the injection site, and skin rash. Hepatic dysfunction, including hepatitis and cholestatic jaundice, has been associated with the use of sulbactam. Hepatic toxicity is usually reversible; however, deaths have been reported. Routine monitoring of liver function will be conducted at baseline and during and after administration of ETX2514SUL.

Dose adjustments are necessary for severe renal insufficiency and hemodialysis patients. It is expected that the combination of ETX2514SUL with imipenem/cilastatin will have high levels of penetration in the lung and, hence, should show good efficacy in treatment of patients with ABC pneumonia. Reproductive studies for ETX2514 have not yet been completed, so precautions against exposure in pregnant women and avoidance of pregnancy of participants in this study are necessary. Allergic and hypersensitivity reactions are a potential risk, as with all antimicrobials, and patients with serious known allergies to BLs will not be enrolled in the study.

Colistin is now used routinely for Gram negative infections that are resistant to carbapenems, based on treatment guidelines in most countries with high prevalence of such infections. The risk of nephrotoxicity and neurotoxicity are well described in the colistin label and the literature. Dosing of colistin in this trial is weight-based and will be adjusted based on daily calculations of estimated glomerular filtration rate (eGFR). Patients will be monitored for worsening renal function and

signs of neurotoxicity. Patients with contraindications for colistin treatment may be considered for enrollment in Part B of the study.

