### 4.3 Withdrawal and Discontinuation Criteria

Participation of a patient in this clinical study may be withdrawn or study drug discontinued by the patient or Investigator for any of the following reasons:

- The patient withdraws consent or requests discontinuation from the study for any reason;
- Occurrence of any medical condition or circumstance that exposes the patient to substantial risk and/or does not allow the patient to adhere to the requirements of the protocol;
- Any SAE, clinically significant adverse event, severe laboratory abnormality, intercurrent illness, or other medical condition which indicates to the Investigator that continued participation is not in the best interest of the patient;
- Patient develops severe liver-related abnormalities, as detailed below:
  - ALT or AST  $>10 \times$  ULN;
  - ALT or AST  $>5 \times$  ULN for more than 2 weeks or progressively increasing transaminases despite clinical improvement of underlying infection;
  - Confirmed values of ALT or AST  $>3 \times$  ULN and total bilirubin  $>2 \times$  ULN or international normalized ratio  $>1.5$  (for patients who are not on coumadin) without evidence of an alternative etiology; or
  - Confirmed values of ALT or AST  $>3 \times$  ULN along with signs or symptoms compatible with hepatitis or hypersensitivity (eg, fatigue, nausea, vomiting, right upper quadrant pain or tenderness, jaundice, fever, rash, or eosinophilia [ $>5\%$ ]);
- Pregnancy;
- Requirement of prohibited concomitant medications, including the need for antibiotics that have an overlapping Gram negative coverage other than study drugs;

Note: Patients who require antibiotic prophylaxis due to immunosuppression (eg, trimethoprim-sulfamethoxazole for prophylaxis against *Pneumocystis carinii* [*P. carinii*] pneumonia) may participate in the study.

- Patients randomized to Part A based on a positive screening of a respiratory sample for ABC by BPP rapid test, but subsequently do not have growth of ABC in their respiratory sample culture processed by the local microbiology laboratory;
- Patient failure to comply with protocol requirements or study-related procedures, including the need for treatment with study drug beyond 14 days; or
- Termination of the study by the Sponsor or the regulatory authority.

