## **8 SAFETY ASSESSMENTS**

### **8.1 Adverse Events**

An adverse event is defined as any untoward medical occurrence in a clinical investigation patient administered a pharmaceutical product, which does not necessarily have a causal relationship with this treatment. An adverse event can therefore be any unfavorable and/or unintended sign (including an abnormal laboratory finding), symptom, or disease temporally associated with the use of an investigational medicinal product, whether or not related to the investigational medicinal product. All adverse events, including observed or volunteered problems, complaints, or symptoms, are to be recorded on the appropriate eCRF.

Adverse events, which include clinical laboratory test variables, will be monitored and documented from the time of the main informed consent (not the limited scope ICF) until study participation is complete. This is to be understood that Investigators should report any adverse event occurring from the time the main ICF (including all study procedures) was signed. Investigators are not required to report adverse events occurring for patients who only signed the limited scope ICF (which only allows rapid testing on a respiratory sample). Patients should be instructed to report any adverse event that they experience to the Investigator. Beginning at enrollment, Investigators should make an assessment for adverse events at each visit and record the event on the appropriate adverse event eCRF.

Wherever possible, a specific disease or syndrome rather than individual associated signs and symptoms should be identified by the Investigator and recorded on the eCRF. However, if an observed or reported sign or symptom is not considered a component of a specific disease or syndrome by the Investigator, it should be recorded as a separate adverse event on the eCRF. Additionally, the condition that led to a medical or surgical procedure (eg, surgery, endoscopy, tooth extraction, or transfusion) should be recorded as an adverse event, not the procedure.

Any medical condition already present at Screening should not be reported as an adverse event unless the medical condition or signs or symptoms present at baseline changes in severity or seriousness at any time during the study. In this case, it should be reported as an adverse event.

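### Protocol Sections 7.5 and 8.1 give conflicting adverse event rules for signs of the presenting infection, so a Table 3 sign caused by study drug may get no AE record or causality assessment

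*Protocol*

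**What the plan says.** Protocol Section 7.5 sets up a regular bedside assessment: "Clinical signs and symptoms of the presenting indication will be assessed at Screening, daily during IV treatment beginning on Day 1". It continues through the follow-up visits, and Table 3 lists the signs for each indication. On safety reporting it says: "Findings from the assessment of signs and symptoms will be captured on the appropriate eCRF and should not be documented as adverse events". No exception follows for a sign that is new, worse, or thought to be due to study drug.

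Section 8.1 starts from the opposite default: "All adverse events, including observed or volunteered problems, complaints, or symptoms, are to be recorded on the appropriate eCRF". A condition already present at Screening is not an AE "unless the medical condition or signs or symptoms present at baseline changes in severity or seriousness at any time during the study". It continues: "In this case, it should be reported as an adverse event". Section 8.1 also prefers a diagnosis to its component signs, and asks for a separate AE "if an observed or reported sign or symptom is not considered a component of a specific disease or syndrome by the Investigator". It ends by saying that clinical failures are not AEs.

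SAP Section 6.1 repeats the rule that all AEs are recorded and does not repeat the exclusion in 7.5.

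**The concern.** Some Table 3 signs are also possible drug effects, and the protocol treats several of them that way. Section 1.4 includes nausea and vomiting among the less common treatment-emergent events seen in patients, and says of a marketed sulbactam combination: "The most frequently reported adverse events reported with Unasyn are nausea, vomiting, diarrhea, pain at the injection site, and skin rash". Section 4.3 pairs raised transaminases with "signs or symptoms compatible with hepatitis or hypersensitivity (eg, fatigue, nausea, vomiting", and its list goes on to include fever.

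Causality is assessed on adverse events (Protocol Sections 5.4.1, 5.4.2 and 8.1.3). A finding kept off the AE form therefore never reaches the step meant to separate drug effect from infection. With approximately 100 sites and two rules, the same event can be recorded differently from site to site. Comparing safety with colistin and describing the ETX2514SUL safety profile are both secondary objectives.

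**Working it through.** No arithmetic applies, so the check sets the rules side by side.

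**Step 1. What each section requires for a Table 3 finding**

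| Finding | Section 7.5 | Section 8.1 | Agree? |
|---|---|---|---|
| Present at baseline, stable or improving | Not an AE | Not an AE | Yes |
| Worse than baseline, infection not responding | Not an AE | AE by the worsening clause; not an AE if it amounts to clinical failure | Unclear, also within 8.1 |
| Worse than baseline, not attributed to the infection | Not an AE | AE by the worsening clause | No |
| New after dosing, not attributed to the infection | Not an AE | AE by the general rule | No |

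The direct conflict lies in the last two rows. The second row also needs wording, because the worsening clause and the clinical-failure sentence in 8.1 pull in different directions.

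**Step 2. Which signs and patients are exposed**

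The rule in 7.5 reaches only the signs of the patient's own presenting indication. Mapping the overlapping signs to Table 3, the Part A and Part B entry criteria (Sections 4.1.2 and 4.1.3) and the vital-sign plan (Protocol Section 8.7, SAP Section 9.4.3) gives:

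| Sign | Table 3 indications | Part | In the planned vital-sign summary? |
|---|---|---|---|
| Fever | All | A (both arms) and B | No; temperature is not listed |
| Dyspnea | Non-ventilated pneumonia | A and B | No; respiratory rate is |
| Systolic pressure below 90 mmHg | Bacteremia | A and B | Yes |
| Heart rate above 100 | Bacteremia | A and B | Yes |
| Respiratory rate above 25 | Non-ventilated pneumonia, bacteremia | A and B | Yes |
| Nausea, vomiting | cUTI/AP | B only | No |

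**Step 3. Whether another planned table would recover the finding**

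SAP Section 9.4 plans no safety summary of the signs-and-symptoms form. Section 7.5 does have the maximum daily temperature recorded, so fever data will exist, but no planned safety output uses them. Blood pressure, heart rate and respiratory rate are summarised and listed. That shows the measurement, but gives no causality assessment.

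**Step 4. What is untouched**

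- The primary endpoint is death from any cause.
- The RIFLE categories are defined by creatinine, GFR and renal failure, none of which is a Table 3 sign.
- The SAE rule in Section 8.3 contains no Table 3 exclusion.

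**The case against.** The strongest defence is that 7.5 concerns manifestations of the infection under study, and that keeping those out of the AE data is sound. Section 8.1 partly agrees, since it prefers a diagnosis to its component signs and excludes clinical failure. This stands for signs that are stable, improving or attributed to the infection. It does not settle a sign on the Table 3 list that has another cause, because 7.5 excludes the findings of the assessment without asking about cause.

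A reader might infer that drug-related nausea, vomiting, fever, dyspnea and hypotension never reach the TEAE, SAE or special-interest tables. The documents do not support that:

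- A hypersensitivity reaction can be recorded under 8.1 as a diagnosis, and that diagnosis is not a Table 3 sign. The other special-interest categories are not Table 3 signs either.
- Section 8.3 carves nothing out of SAE reporting.
- Nausea and vomiting are not Table 3 signs for any Part A indication, so the comparison with colistin does not lose them.
- Dyspnea and low systolic pressure are each confined to one indication group, and blood pressure is still summarised.

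The supporting citations are also limited. The Unasyn sentence concerns ampicillin/sulbactam. Section 1.4 lists nausea and vomiting as treatment-emergent without calling them drug-related. The liver criterion in 4.3 rests on transaminases together with symptoms, and does not depend on an AE entry.

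It might also seem enough to make every new or worse Table 3 sign an AE. That would collide with the sentence in 8.1 that clinical failures are not AEs.

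**Conclusion.** The conflict is real but narrow. For a Table 3 sign that worsens or appears on treatment and is not attributed to the index infection, 7.5 says no AE and 8.1 says AE, with nothing to say which prevails. If 7.5 is followed, the finding has no AE record and no causality assessment. Fever is the main exposure in the randomized comparison, because it is on the list for every indication and temperature is missing from the planned vital-sign summary. Dyspnea and low systolic pressure are smaller exposures limited to one indication group each. Nausea and vomiting matter only for the Part B safety profile in cUTI/AP.

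The size of the loss cannot be derived. The documents give neither rates for these drug effects in the trial's indications nor a planned number of cUTI/AP patients. The conclusion assumes that at least some sites apply 7.5 as written; a site that applies 8.1 would lose nothing. The mortality, RIFLE and SAE reporting rules stand as they are.

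**What to change.** Replace the sentence in Protocol Section 7.5 with wording such as:

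> Signs and symptoms in Table 3 that the assessor attributes to the index ABC infection, including those that constitute clinical failure, are recorded only on the signs/symptoms eCRF. A Table 3 finding that is new or worse than baseline and is not attributed to the index infection (including one possibly related to study drug), or that meets a seriousness criterion, is also reported under Sections 8.1 to 8.3.

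Then align the worsening clause and the clinical-failure sentence in Section 8.1 with this text, so that both sections draw the line at attribution to the index infection.

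The cost is a short protocol change and a memo to sites, some additional AE reports, and an attribution judgment that sites must make and document. No efficacy endpoint or treatment rule changes.
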